2.3 Experiment timeline

We began sample recruitment on 24 January 2025. We expect to collect primary outcomes by the end of April 2025, but this may vary as we rely on the college administration to schedule our visits to classrooms. This pre-analysis plan was posted soon after the beginning of data collection. In the paper, as a robustness check, we will report results for data collected solely after the pre-analysis plan was posted.

3 Outcomes

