2.2 Treatments

Treatments are randomized at the individual level, stratified by categories of PHQ-ADS scores. Treatment status will be revealed via the survey administered through students' mobile phones. Participants will be randomized to four conditions:

1. **Control:** The control group will (a) watch a video introducing them to the mental health services available in the college, including introductory videos of the counselors, (b) have access to therapy at no cost for the duration of the study via their college counselors and additionally at SCARF, a mental health center in Chennai, and (c) be given links to book a therapy session or download a mental health app.
2. **Screening:** In addition to the interventions in the control group, students in the screening group will receive feedback on their PHQ-ADS score and recommendations based on that. In particular, they will be informed whether their responses to the PHQ-ADS questions fit in the standard risk categories of no, mild, moderate, or severe distress and corresponding recommendations for whether to make an appointment with a counselor/therapist.
3. **Rewards:** In addition to the interventions in the control group, students in the rewards group will be provided with a cash payment of Rs. 500 (USD 5.70 at market exchange rates) for attending a (first) therapy session.
4. **Screening and rewards:** Students in this group will receive both interventions, i.e., both the screening information and the reward described above.

For ethical reasons, participants with PHQ-ADS scores of 30 or above (indicating severe risk of depression and anxiety) in the non-screening treatment arms will also be informed of their scores at the end of the survey. For outcome variables measured within the survey, we will treat these participants as though they are part of the group to which they are randomly assigned. One outcome variable (completing the process to make an appointment for therapy) is measured after the conclusion of the participant survey. For this outcome variable, we will separately run regressions both including and excluding these individuals.

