3.1 Primary Outcomes

We have two primary outcomes:

1. **Expressing interest in therapy.** This consists of students answering “yes” when asked in the survey if they would like to book an appointment with a counselor, or if students answer “yes” when asked in the survey if they would like to be contacted by a study counselor to discuss mental health and therapy.
2. **Making an appointment.** If a student actually makes an appointment with a counselor (measured using the administrative records from the counseling offices)

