3.2 Secondary Outcomes

The secondary outcomes of the study include the following:

1. **Take-up of mental health app.** This is measured in two ways: participants expressing interest in accessing a mental-healthcare app in the survey, and participants actually clicking a link to download the app.
2. **Demand for information about mental health.** This is measured in two ways: participants expressing interest in receiving more information about mental health, and participants actually clicking a link to access the information.
3. **Attendance of therapy sessions.** We will collect data from the administrative records of the counselling office on whether participants actually attended a therapy session, as well as the number of sessions attended.
4. **Other variables.** We will also report exploratory analyses and mechanism tests including: (i) whether participants report in the survey if they would consider seeking therapy in future; (ii) what steps they report they would take to take care of their mental health in future; (iii) reported motivating/inhibiting factors for taking up therapy and perceptions of therapy.

4 Empirical analysis

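### Do appointment, attendance and session count need a stated per-student follow-up window, given rolling enrolment?

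*Combined protocol and SAP*

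**What the plan says.** Section 2.3 (Experiment timeline) gives the start, "We began sample recruitment on 24 January 2025", and a movable end: "We expect to collect primary outcomes by the end of April 2025, but this may vary". The rest of that sentence ties the uncertainty to the scheduling of classroom visits.

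Section 3.1 (Primary Outcomes) defines the second primary outcome as "If a student actually makes an appointment with a counselor (measured using the administrative records from the counseling offices". Section 2.2 (Treatments) says that this outcome "is measured after the conclusion of the participant survey". Section 3.2 (Secondary Outcomes) adds, again from office records, "whether participants actually attended a therapy session, as well as the number of sessions attended".

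All arms "have access to therapy at no cost for the duration of the study" (section 2.2). For robustness, section 2.3 says "we will report results for data collected solely after the pre-analysis plan was posted".

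No section gives a follow-up length per student, a last-enrolment date or a date for pulling the records. The controls listed in section 4.1 do not include enrolment date or time at risk.

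**The concern.** Whether a student has booked, or how many sessions she has attended, depends on how long one looks. Under a single calendar cutoff, a student surveyed on the first day would have 96 days to book and one surveyed on the last day almost none. Late recruits who would have booked could be coded zero. That could shrink absolute effects on one of the two primary outcomes, cost power and make the estimate depend on the visit calendar. Session count looks most exposed, because sessions take calendar time however quickly the first is booked. The cutoff could also be chosen with results in view. Finally, the robustness check on post-plan data could be read by survey date or by record date.

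**Working it through.** The plan states no booking rate, delay, sample size or power, so it has no figure of its own to reproduce. What follows is a range under assumptions.

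**From the plan.** Recruitment started on 24 January 2025 and collection is expected to end by the end of April. To 30 April that is 96 days. From the plan's date, 12 February (taken as the posting date), it is 77 days.

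**Assumed.** Enrolment is uniform, all records are extracted on 30 April, and the delay from survey to booking is exponential with mean μ, the same in every arm.

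**Bookings missed.** For follow-up uniform on [a, b] days, the missed share is m = μ/(b−a) × (exp(−a/μ) − exp(−b/μ)). For μ = 7 on [0, 96]: 7/96 × (1 − exp(−96/7)) = 7.3%.

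| Mean delay (days) | 1 | 3 | 7 | 14 | 30 |
|---|---|---|---|---|---|
| Enrolment to the cutoff, [0, 96] | 1.0% | 3.1% | 7.3% | 14.6% | 30.0% |
| Enrolment ends 21 days earlier, [21, 96] | 0.0% | 0.0% | 0.5% | 4.1% | 18.2% |

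**Effective sample size.** With an assumed eventual booking rate p = 0.10 and q = p(1−m), the factor is (1−m)² p(1−p) / (q(1−q)). On [0, 96] the loss is 1.2%, 3.5%, 8.0%, 15.9% and 32.2% across the five delays. On [21, 96] it is 0.5%, 4.6% and 19.9% at 7, 14 and 30 days.

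**Session count.** Suppose four weekly sessions at 7, 14, 21 and 28 days after booking, with μ = 3 (a pattern not in the plan). On [0, 96] the session at k days is missed with probability close to (k + 3)/96: 10.4%, 17.7%, 25.0% and 32.3%, mean 21.4%. On [21, 96] the four are 3/75 × exp(−14/3) = 0.04%, 3/75 × exp(−7/3) = 0.39%, 3/75 = 4.0% and (7 + 3)/75 = 13.3%, mean 4.4%.

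**Direction.** Now let delays differ by arm. Suppose 10% eventually book in both arms, with median delay 7 days under rewards and 21 days otherwise. The means are 7/ln 2 = 10.1 and 21/ln 2 = 30.3 days. The shares captured on [0, 96] are 89.5% and 69.8%. The observed difference is 10% × (0.895 − 0.698), about 2.0 points, where the eventual difference is zero. Truncation can therefore enlarge an effect as well as shrink it.

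**Would a fixed window do better?** A window of W days misses exp(−W/μ).
- W = 30 misses 1.4%, 11.7% and 36.8% at mean delays of 7, 14 and 30 days. At 30 days that is worse than the 30.0% under the calendar cutoff.
- W = 48 equals the mean follow-up on [0, 96], so there it never does worse than the cutoff. On [21, 96] with μ = 30 it misses 20.2% against 18.2%.
- W = 60 misses 0.0%, 1.4% and 13.5%, better than the cutoff in both settings. In the speed-up example it still shows 10% × (exp(−60/30.3) − exp(−60/10.1)), about 1.4 points.

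**Post-plan check.** By survey date, follow-up is uniform on [0, 77] and m is 9.1%, 18.1% and 36.0% at 7, 14 and 30 days. The ratio of post-plan to full-sample effect is (1 − 0.091)/(1 − 0.073) = 0.98, then 0.96 and 0.91. This again assumes equal delays across arms.

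**The case for a change.** The best case for a change is that one of the two primary outcomes lacks a time horizon, and a pre-analysis plan exists to fix such choices before results are seen. The wording would cost little. The dependence of direction on booking speed can be added to that case: without a horizon, a reader cannot say which way the estimate leans. Attendance and session count are weaker still, because the end-of-April expectation covers primary outcomes only.

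Much of this stands as a description. The horizon is not written down, and stating one would make the report clearer. What does not stand is the step from a missing detail to a wrong result. The larger losses need three things together: enrolment up to the extraction day, delays of weeks, and equal delays in every arm. The plan states none of them. It links the movable end date to classroom visits, so later visits would plausibly move the records pull later too. Every arm is given booking links in the survey, which makes short delays plausible for many students, although the route through contact by a counselor may be slower. A fixed window is also not a clear gain: a short one can miss more bookings than a common cutoff, and a longer one targets a slightly different quantity without removing the speed-up effect.

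**Conclusion.** The omission is real and minor, and the plan can stand. Because assignment is individual, time at risk has the same expected distribution in each arm. Comparing appointments, attendance or sessions by the end of the study is a legitimate intention-to-treat contrast, and the first primary outcome is not affected at all.

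Missed bookings are about 3% or less if the mean delay is up to 3 days, whatever the gap between last enrolment and extraction. They are 4.1% or less at mean delays up to 14 days with a 21-day gap. They reach 30.0% only with month-long mean delays and no gap. These figures rest on assumed uniform enrolment and exponential delays, and neither their size nor their direction can be derived from the documents.

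Analysts can be expected to pull the records some time after the last visit, report the date and, if they wish, show bookings within a common number of days as a supplement. For the post-plan check, survey date is the natural reading. Under equal delays it moves the effect by roughly 2% to 9% at mean delays of 7 to 30 days, and it concerns a robustness analysis only.

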3.1 Primary Outcomes

We have two primary outcomes:

1. **Expressing interest in therapy.** This consists of students answering “yes” when asked in the survey if they would like to book an appointment with a counselor, or if students answer “yes” when asked in the survey if they would like to be contacted by a study counselor to discuss mental health and therapy.
2. **Making an appointment.** If a student actually makes an appointment with a counselor (measured using the administrative records from the counseling offices)

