4.1 Main regression specification

Pooled treatment effects. Our main specification will be a linear regression of outcomes on the ‘pooled’ treatment assignment, separately for the screening treatment and rewards treatment. That is, define

$$\begin{aligned} \text{Pooled screen}_i &= \text{Screen}_i + \text{Screen and rewards}_i \\ \text{Pooled rewards}_i &= \text{Rewards}_i + \text{Screen and rewards}_i, \end{aligned}$$

where Screen_i is an indicator variable for i being assigned to the screening group, Rewards_i is an indicator variable for i being assigned to the rewards group, and $\text{Screen and rewards}_i$ is an indicator variable for i being assigned to the combined screening and rewards group.

To identify the effect of the pooled treatments on the outcome variables, we will run the following regression specification, separately for each pooled treatment and outcome variable:

$$Y_i = \alpha + \beta T_i + X_i' \lambda + \epsilon_i$$

where Y_i represents the outcomes for individual i described above, $T_i \in \{\text{Pooled screen}_i, \text{Pooled rewards}_i\}$ represents the pooled treatment indicators described above. X_i is a vector of controls consisting of the limited set of variables collected in the survey prior to treatment. This includes categories of PHQ-ADS scores (no risk, mild risk, or moderate-to-severe risk), whether participants report that their family would be supportive of seeking therapy, their current mood, their perception of their current and previous mental health and well-being, whether they have received mental health care in the past, interest in therapy at baseline, and a measure of their financial status.

Fully saturated model. For each outcome, we will also report a “saturated” regression which breaks up the effects by each of the treatment cells:

$$Y_i = \alpha + \beta_1 \text{Screen}_i + \beta_2 \text{Reward}_i + \beta_3 \text{Screen and Reward}_i + X_i' \lambda + \epsilon_i$$

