4.2 Heterogeneity analysis

Heterogeneity by baseline mental health status. For our primary outcome and for selected secondary outcomes such as take-up of the app, we will analyze heterogeneity by baseline mental health status, as measured by the PHQ-ADS. This heterogeneity is policy-relevant, because policy-makers may especially value students at high risk of anxiety and depression receiving therapy. It also conceptually relates to our treatments, in that screening might be expected to cause more positive selection on symptoms of depression and anxiety while rewards have ambiguous selection effects.

The standard cutoffs in scores in the PHQ-ADS scale in the literature are 10-19 for mild symptoms, 20-29 for moderate symptoms, and 30 or higher for severe symptoms. We will combine the moderate and severe categories in our analysis, as only a small share of students are expected to show severe symptoms.

We will estimate the following regression:

$$Y_i = \alpha + \beta T_i + \gamma T_i \times \text{Mild}_i + \theta T_i \times \text{Moderate or Severe}_i + \lambda X'_i + \epsilon_i$$

for each of the pooled treatment indicators and outcome variables. The vector of controls X_i includes the indicator variables Mild_i and $\text{Moderate or Severe}_i$.

We will also run a model which interacts the treatments with a continuous measure of the PHQ-ADS score:

$$Y_i = \alpha + \beta T_i + \gamma T_i \times \text{PHQ-ADS}_i + \lambda X'_i + \epsilon_i$$

where X_i is the vector of controls now including the continuous measure of PHQ-ADS score.

Heterogeneity by other characteristics. As exploratory analyses, we will examine heterogeneity by other baseline characteristics, such as participants' financial status, their perception of their mental health status, and their major sources of stress.

Heterogeneity by other characteristics.

5 Funding and Human Subjects Review

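### The exclusion version of the appointment regression drops severe scorers from one side of the screening contrast only, so it should be made symmetric and labelled sensitivity; the plan also states no alpha or test family for its two primary outcomes.

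*Combined protocol and SAP*

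**What the plan says.** Section 2.2 explains that, for ethical reasons, participants with PHQ-ADS scores of 30 or above "in the non-screening treatment arms will also be informed of their scores at the end of the survey". Making an appointment is measured after the survey, so this disclosure can affect it. For that outcome the plan says "we will separately run regressions both including and excluding these individuals". On its wording, the group to be left out is the severe scorers in the control and rewards arms. Severe scorers in the two screening arms are not mentioned. Neither version is labelled as the lead.

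Section 4.1 sets the main specification: a linear regression on a pooled treatment indicator, run "separately for each pooled treatment and outcome variable". Its controls include "categories of PHQ-ADS scores (no risk, mild risk, or moderate-to-severe risk"). Section 4.2 confirms the merging ("We will combine the moderate and severe categories in our analysis") and gives the reason that "only a small share of students are expected to show severe symptoms".

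Section 3.1 says "We have two primary outcomes": expressing interest in therapy, and making an appointment. With two pooled treatments this gives four main coefficients. No section states a significance level, a family of tests, an adjustment or a testing order.

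**The concern.** Randomisation makes the screening and non-screening arms comparable in severity. Removing severe scorers from only one of those sides undoes this by design. A control that distinguished severe from moderate would repair it, but the planned control puts them in one category. Within that category, the screening side is a mix of moderate and severe students, and the non-screening side is moderate only. If severe students book more often for reasons unrelated to screening, that version of the regression shows a screening effect where none exists. If they book less often, it hides or reverses one.

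The saturated model has the same problem under the exclusion. The control and rewards cells lose their severe scorers, so the screening and combined coefficients, both measured against control, inherit the imbalance.

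The two versions may disagree, and the plan does not say which then takes precedence. Separately, with no alpha or family stated, a reader cannot tell what evidence on two primary outcomes would count as a primary finding.

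**Working it through.** The plan gives no figure to reproduce: it states no power calculation, sample-size target, allocation ratio, booking rate or share of severe students. Every rate below is an assumption.

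**Inputs assumed.** 1,000 students; equal allocation to four arms; 30% mild, 20% moderate, severe share varied, the rest no risk. Booking is 8% for none and mild, 12% for moderate and 30% for severe. There is no true treatment effect, and PHQ-ADS category (none, mild, moderate-to-severe) is the only control.

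**Bias of the one-sided exclusion, pooled screening.** In the merged category the screening side has 100 moderate students plus half of all severe students; the non-screening side has 100 moderate students. Then

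- gap = (severe / (moderate + severe) on the screening side) × (severe booking − moderate booking);
- weight of a category = n1·n0/(n1 + n0), divided by the sum over the three categories;
- bias = gap × weight of the merged category.

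| Severe share | Gap (points) | Weight of merged category | Bias (points) | Null rejection, simulated |
|---|---|---|---|---|
| 2% | (10/110) × 18 = 1.64 | 52.4/(52.4+120+75) = 0.212 | +0.35 | about 5-6% |
| 3% | (15/115) × 18 = 2.35 | 53.5/(53.5+117.5+75) = 0.217 | +0.51 | about 5-6% |
| 5% | (25/125) × 18 = 3.60 | 55.6/(55.6+112.5+75) = 0.229 | +0.82 | about 8% |
| 10% | (50/150) × 18 = 6.00 | 60/(60+100+75) = 0.255 | +1.53 | about 12% |

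Simulation with robust standard errors gives matching biases (for example +0.83 at 5% severe and +1.50 at 10%).

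**Sensitivity to the booking rates.**
- Severe booking 20%, 5% severe: (25/125) × 8 × 0.229 = +0.37 points, rejection about 5.4%.
- Severe booking 6%, 10% severe: (50/150) × (−6) × 0.255 = −0.51 points, rejection about 5.4%.
- Severe and moderate booking equal: the gap is zero, and so is the bias.

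**Estimates that are not affected.**
- The full-sample pooled-screening regression has bias about 0 and rejection 4.6-5.3% in the runs at 5-20% severe.
- Dropping scores of 30 or above from all arms also gives bias about 0, with rejection 4.8-5.4%.
- Pooled rewards stays balanced even under the one-sided exclusion, because one rewards arm and one non-rewards arm each lose their severe scorers. Simulated bias is within 0.04 points and rejection 4.7-5.6%.

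**Multiplicity (secondary).** Assume each test is two-sided at 5% and all nulls are true. For two outcomes within one treatment, the chance of any rejection is 1 − P(|Z1|<1.96, |Z2|<1.96). This is 1 − 0.95² = 9.75% at outcome correlation 0, 9.1% at 0.5, 7.8% at 0.8 and 5.0% at 1. Taking both treatments as one family, with uncorrelated contrasts, gives 1 − (1 − x)²: 18.5%, 17.3%, 15.0% and 9.75%.

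**The case against.** **The full sample already leads.** Section 4.1 defines the main specification on assigned treatment with no exclusion, and section 2.2 promises both versions, so neither can be withheld. This is a natural reading and most of it stands. A reader might infer that the primary appointment result is itself biased, or that the authors are free to report whichever version suits; the documents support neither. What remains is that the exclusion version is unlabelled, whereas section 2.3 expressly calls its post-posting analysis a robustness check.

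**Few severe students are expected.** Section 4.2 says so, and this limits the size. At 2-3% severe, null rejection hardly moves. Simulated rejection of about 28% is possible at 20% severe, but that share does not fit the plan's own expectation and should not be cited as likely.

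**Other controls may absorb the bias.** Section 4.1 also adjusts for mood, perceived mental health, past care and baseline interest. Adding one assumed binary covariate (prevalence 10/20/40/80% across the four severity levels, +20 points on booking) cut the bias at 10% severe from +1.49 to +0.84 points and rejection from 12.5% to 7.6%. So the controls may help materially, though nothing in the plan ensures it. Rejection also depends on sample size: at 10% severe it is 9.2% with 500 students and 17.2% with 1,500.

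**The exclusion may have been meant for all arms.** If so, the wording needs correcting, and the fix is the same.

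**Multiplicity is partly a matter of choice.** Screening and rewards are separate questions, run separately. The four coefficients are identifiable in advance, and readers could adjust them. This stands. A reader might infer an 18.5% false-positive rate for the trial, but that needs all four coefficients to form one family and the two outcomes to be uncorrelated. Positive correlation is likely, since interest includes saying yes when asked "if they would like to book an appointment with a counselor".

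**Conclusion.** The point holds for one coefficient in one of two promised regressions, pooled screening on appointments with the exclusion, and for the matching screening terms of the saturated model. The imbalance follows from the wording of sections 2.2 and 4.1. The bias needs severe and moderate students to book at different rates. Its size rests on assumed rates: under the main set, +0.3 to +0.5 points at 2-3% severe with rejection close to nominal, +0.8 points and about 8% at 5% severe, and +1.5 points and about 12% at 10% severe. It is smaller if booking rates are closer or other controls absorb severity, and negative if severe students book less. The full-sample pooled-screening estimate and the pooled-rewards estimate are sound in this respect.

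The missing alpha and family are a secondary matter of specification. The relevant range is 5.0-9.75% within one treatment, at an assumed two-sided 5%; the 9.75-18.5% range applies only if all four coefficients are taken as one family.

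The change should be made. Confidence is medium, because the severe share and booking rates are not given.

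**What to change.** 1. Name the as-randomised appointment regression, with everyone included, as the headline.
2. Label the exclusion version a sensitivity analysis, and in it drop participants scoring 30 or above from all four arms. Apply the same rule to the saturated model.
3. State the alpha and the family. Taking the two outcomes within each treatment as the family suits the way section 4.1 poses the questions. Report Holm or Romano-Wolf adjusted p-values beside the unadjusted ones.

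This takes plan wording and a few lines of code, with no new data. There are three costs:
- The headline keeps severe students in the non-screening arms who were told their scores, which may dilute the screening effect among them.
- The symmetric sensitivity analysis avoids that, but speaks only to students scoring below 30 and uses a smaller sample.
- Adjustment loses some power. As an illustration, a test with 80% power at 0.05 has about 71% at the first Holm step (0.025), and one with 90% has about 84%.
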